5.5.13.3 Dermatological Examination

Collected at baseline, Week 60, and EOT visit in the Dermatological Examination eCRF. No definitions and derivations necessary. Any resulting findings are recorded as adverse event (or medical history).

5.5.13.4 Optical coherence tomography

Collected at screening, Week 12, Week 24, Week 60, and EOT visit in the Optical coherence tomography (OCT) eCRF. No definitions and derivations necessary. Any resulting findings are recorded as adverse event (or medical history or relapse).

5.5.13.5 Ophthalmological Examination

Collected at screening, Week 12, Week 24, Week 60, and EOT visit. Data will be taken from both Ophthalmological Examination eCRFs. No definitions and derivations necessary. Any resulting findings are recorded as adverse event (or medical history or relapse).

5.5.13.6 Physical examination

Collected at screening, baseline, Week 4, Week 12, Week 24, Week 60, Week 84, EOT and FUP visit eCRFs. No definitions and derivations necessary. Any resulting findings are recorded as adverse event (or medical history or relapse).

5.5.13.7 Suicidal ideation

The electronic self-rated version of the Columbia-Suicide Severity Rating Scale (eC-SSRS[®]) is an assessment instrument that evaluates suicidal ideation and behavior. During an initial assessment it assesses lifetime as well as the recent history suicidality (scheduled at Visit 2-Baseline), and then prospectively monitors ideations and behaviors at subsequent follow-up assessments since the last call (scheduled at Visit 10-Week 60 and Visit 14-Week 108).

The eC-SSRS outcome categories are provided below. Each category has a binary response (yes/no) and are numbered and ordered below for convenience.

- 1 – Wish to be Dead
- 2 – Non-specific Active Suicidal Thoughts

- 3 – Active Suicidal Ideation with Any Methods (Not Plan) without Intent to Act
- 4 – Active Suicidal Ideation with Some Intent to Act, without Specific Plan
- 5 – Active Suicidal Ideation with Specific Plan and Intent
- 6 – Preparatory Acts or Behavior
- 7 – Aborted Attempt
- 8 – Interrupted Attempt
- 9 – Actual Attempt (non-fatal)
- 10 – Completed Suicide

Furthermore, **self-injurious behavior without suicidal intent** is also an eC-SSRS outcome (although not suicide-related) and has a binary response (yes/no). (Q07a)

The initial assessment has a lifetime and a recent history assessment. The recent history covers the last 1 month for suicidal ideation, and the last 3 months for suicidal behavior. Recent history questionnaire questions are only assessed for outcome categories with corresponding lifetime outcome question answered as yes. If the lifetime assessment for an outcome category is ‘No’, also the corresponding recent history outcome is considered ‘No’ for analysis.

Scoring: Scores are created at each assessment as follows:

- **Suicidal Ideation Score:** The maximum suicidal ideation category (1–5 on the eC-SSRS) present at the assessment. Assign a score of 0 if no ideation is present.
- **Suicidal Behavior Score:** The maximum suicidal behavior category (6–10 on the eC-SSRS) present at the assessment. Assign a score of 0 if no behavior is present.

A subject with multiple reported outcomes for suicidal ideation and suicidal behavior will be summarized under the worst reported outcome (i.e., $\max[1-5]$ and $\max[6-10]$, respectively).

The following definitions will be used:

- **Suicidal ideation:** A “yes” answer to any one of the five suicidal ideation questions (Categories 1-5) on the eC-SSRS. Taken from the ‘Reported most severe ideation level’.

5.6 Quality of life variables

5.6.1 Change from baseline by visit up to Week 108 in SF-36v2™ Health Survey domain and component scores

The SF-36v2™ instrument is a generic health related quality of life assessment provided by the Medical Outcomes Trust, Boston, USA.

It contains 36 items measuring health across eight areas or domains: Physical Functioning (PF, 10 items: #3a – #3j); Social Functioning (SF, 2 items: #6 & #10); Role Limitations due to physical problems (RP, 4 items: #4a – #4d); Role Limitations due to emotional problems (RE, 3 items: #5a – #5c); Mental Health (MH, 5 items: #9b – #9h); Vitality (VT, 4 items: #9a – #9i); Bodily Pain (BP, 2 items: #7 & #8) and General Health perceptions (GH, 5 items: #1, #11a – #11d) and an additional item on reported Health Transition to perceive changes in health status in the past 12 months (HT, 1 item: #2).

In addition, Physical and Mental Component Summary (PCS and MCS) measures are calculated based on aggregate domain scores.

For each of the eight domains, scores will be coded, summed and transformed to generate a score from 0 (worst possible health state) to 100 (best possible health state). These domain scores as well as PCS and MCS will then be standardized to Z scores and then again will be transformed to create norm based scoring also known as t-scores. Details for generating these domain scores and aggregate component scores, handle missing data items and duplicated item entries are given in Appendix C.4.

The SF-36v2™ is completed by the subject on an electronic device at Visit 2 (Baseline), at Visits 6, 7, 10, 12 (Weeks 12, 24, 60, and 84), and 14 (W108) and at unscheduled visits due to relapses (R1, R2, etc.).

For analysis, visits are assigned based on time windowing, as detailed in Section 11.3. Baseline is defined as last available score up to or on randomization date. A variable with LOCF imputation by visit is derived for the domain and aggregated scores.

5.7 Pharmacoeconomic variables

5.7.1 Change from baseline by visit up to Week 108 in Work productivity and activity impairment (WPAI:MS) scores

The WPAI:MS V2.0 assesses work productivity and activity impairment. It has a recall period of 7 days. The following variables are considered:

- **Current paid employment status (Y/N)**

Four WPAI:MS outcome scores are considered that are expressed as impairment percentages, with higher numbers indicating greater impairment and less productivity:

- Percentage of work time missed due to MS (absenteeism),
- Percentage of impairment while working due to MS (presenteeism),
- Percentage of overall work impairment due to MS,
- Percentage of activity impairment due to MS.

The first three of these outcomes will be calculated only for those subjects who are working for pay, and the last outcome will be calculated for all subjects. See Appendix C.5 for details on the scoring.

WPAI is completed by the subject on an electronic device at Visit 2 (Baseline), and at Visits 6, 7, 10, and 12 (Weeks 12, 24, 60, 84, respectively), 14 (Week 108). For analysis, visits are assigned based on time windowing, as detailed in Section 11.3.

Absolute change from baseline is derived with baseline defined as last available score up to and including randomization date.

5.7.2 Health care resource utilization from baseline up to Week 108

Health care resource utilization data is taken from the following CRF pages: Hospitalization as recorded on the Adverse events, and 'Relapse summary' forms. Intensive care unit admissions for MS relapses are taken from 'Intensive Care Unit Admissions for MS Relapses' form. Emergency room visits for MS are taken from the 'Emergency medical facility visits for MS' form.

The following health care resource utilization variables will be derived:

- Number of admissions / visits from baseline to Week 108 (Frequency of health care resource utilizations)
- Length of stay (days) from baseline to Week 108 (Duration of health care resource utilizations)

The variables above are derived for the following categories

- Any hospitalization: Derived from the Adverse event, Relapse summary and ‘Intensive Care Unit Admissions for MS Relapses eCRFs.
- Hospitalizations due to AEs: Derived from the AE page
- Hospitalizations due to relapses: Derived from the Relapse summary eCRF
- Intensive Care Unit (ICU) admissions for MS Relapses: Derived from the ‘Intensive Care Unit Admissions for MS Relapses’ form and includes all admissions (irrespectively if due to MS relapse or due to MS)
- Emergency room visits for MS relapses: Derived from the ‘Intensive Care Unit Admissions for MS Relapses’ form and includes visits due to MS relapse and due to MS. Note that emergency room visits are not considered hospitalizations.

The length of stay (in days) per admission is defined as: Length of hospitalization = End date of hospitalization – Start date of hospitalization + 1 (in days).

The length of stay (in days) from baseline to Week 108 per category taking into account multiple encounters is derived as the sum of length of stay across all admissions / visits only considering days from baseline (randomization date) to Week 108 (Day 756). In case of overlapping hospitalizations, each day is counted only once.

The number of admissions / visits from baseline to Week 108 is defined as a count variable per category. Two hospitalizations with identical admission date will be counted as one hospitalization.

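### SAP 5.7.2 derives emergency room visits from the ICU-admissions form, although the same section names a separate emergency-facility form as their source

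*SAP*

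**What the plan says.** Section 5.7.2 of the SAP first lists the CRF pages that supply the resource-use data. Two of its statements matter here:

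- For ICU stays: "Intensive care unit admissions for MS relapses are taken from 'Intensive Care Unit Admissions for MS Relapses' form".
- For emergency visits: "Emergency room visits for MS are taken from the 'Emergency medical facility visits for MS' form".

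The section then defines two variables, number of admissions or visits and length of stay, and gives a derivation rule for each category:

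- The overall category: "Any hospitalization: Derived from the Adverse event, Relapse summary and" the ICU-admissions form.
- The ICU category is taken from the ICU-admissions form; the bullet continues "form and includes all admissions (irrespectively if due to MS relapse or due to MS".
- The emergency category: "Emergency room visits for MS relapses: Derived from the" same ICU-admissions form, covering visits for relapses and also those due to MS more generally.

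The emergency bullet closes with a note: "Note that emergency room visits are not considered hospitalizations".

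Section 9.12.2 plans descriptive statistics on the FAS for frequency and length of stay, with ICU admissions and emergency room visits as separate categories.

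**The concern.** The source list and the derivation rule for the same category name different forms, and both cannot be followed. The derivation rule is the text that a programmer implements and that a validator checks the output against, and it is the one that appears to be wrong. An output that matches the written rule would pass validation yet report ICU stays under the heading of emergency visits. The emergency visits actually collected would be missing from the planned summary.

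**Working it through.** No arithmetic applies: the SAP gives no figure for these variables. The check is a comparison of the statements in Sections 5.7.2 and 9.12.2.

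| Category | Source list (5.7.2) | Derivation rule (5.7.2) | Planned display (9.12.2) |
|---|---|---|---|
| ICU admissions | ICU-admissions form | ICU-admissions form | Own category |
| Emergency room visits | Emergency-facility form | ICU-admissions form | Own category |
| Any hospitalization | AE and Relapse summary forms | AE, Relapse summary and ICU-admissions forms | Own category |

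1. **Source.** The ICU row is consistent across the section. The emergency row is not. The emergency-facility form appears once, in the source list, and in no derivation rule.

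2. **Scope.** The ICU bullet takes every admission on its form, whether due to a relapse or to MS. The emergency bullet takes visits due to a relapse and visits due to MS. With the same form and the same scope, the two categories select the same records, so the emergency row would repeat the ICU row in each arm for both variables.

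3. **Consistency with the hospitalization note.** ICU-form records feed any hospitalization. Under the written rule the same records would also be emergency visits, which the SAP says are not hospitalizations. The note makes sense only if emergency visits come from a different form, which supports the source list as the intended text.

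4. **Other explanations.** Nothing in the SAP says that the ICU form also records emergency visits. The text is complete at this point, with no redaction or broken table, and the document history in Appendix E mentions nothing that bears on it. A form name carried over from the bullet above is the likeliest cause.

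5. **Labels.** The category is limited to MS relapses in the name given by the derivation bullet, but is described as being for MS in the source list and due to MS in Section 9.12.2. The bullet's own content covers both, so its name is narrower than its definition.

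**The case against.** The best case on the other side is that the intent is plain. The section opens by naming the emergency-facility form, the same bullet separates emergency visits from hospitalizations, and Section 9.12.2 lists the two categories separately. A careful programmer would notice the clash and use the right form, so the error may never reach a table. The reach is also small: the summary is descriptive, has no test or model, and lies outside the testing strategy in Section 9.1. The clash with the hospitalization note is the same wrong form name seen from another side, and adds no separate harm.

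Most of this stands. The wrong result follows only if the bullet is programmed literally, and the harm is limited to one category. It does not remove the defect. An analysis plan should not leave a programmer to choose between two named sources, and here the literal reading of the operative rule is the one that fails.

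**Conclusion.** The derivation rule for emergency room visits is wrong as written. Followed literally, it replaces the whole emergency-visit category, in both arms and for both frequency and length of stay, with ICU records, and leaves the emergency-facility data unused. ICU admissions, hospitalizations due to AEs or relapses, and any hospitalization keep their own sources and are unaffected. No efficacy or safety inference is touched.

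The conclusion rests on two assumptions: that the emergency-facility form exists as the source list describes it, and that the ICU form does not also capture emergency visits. The SAP supports the first and gives no hint against the second; the CRF itself was not available to confirm either. How far the reported numbers would be off depends on how many ICU stays and emergency visits occurred, which the SAP does not give.

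**What to change.** In the emergency room bullet of Section 5.7.2, replace the ICU-admissions form with the emergency-facility form already named in that section's source list, after a quick check against the CRF. In the same edit, use one label for the category in the source list, the derivation bullet and Section 9.12.2, so that the name matches the stated scope of visits due to MS relapse and due to MS.

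The cost is one form name and one label. Data collection, analysis sets and methods stay as they are.

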9.12.2 Health care resource utilization

Health care resource utilization will be summarized and listed on the FAS.

Descriptive summary statistics will be displayed for subjects with at least one and frequency of health care resource utilizations as well as length of stay (days) from baseline up to Week 108 for the following categories: all hospitalizations, hospitalizations due to AE, hospitalizations due to relapse, ICU admissions due to MS relapses, emergency room visits due to MS.

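### In SAP 5.7.2 the count of hospitalizations merges records only when admission dates are identical, so an overlapping record with a later start date turns one continuous stay into two

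*SAP*

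**What the plan says.** SAP 5.7.2 derives two variables for each category of resource use: a number of admissions or visits, and a length of stay in days. The pooled category is defined as "Any hospitalization: Derived from the Adverse event, Relapse summary and" the form for ICU admissions for MS relapses, so it has three sources. ICU admissions also form a separate category. The one exclusion stated is "Note that emergency room visits are not considered hospitalizations".

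Duplicate records are handled differently for the two variables:

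- Length of stay: "In case of overlapping hospitalizations, each day is counted only once".
- Number: "The number of admissions / visits from baseline to Week 108 is defined as a count variable per category", followed by "Two hospitalizations with identical admission date will be counted as one hospitalization".

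Section 9.12.2 describes the output on the FAS: "Descriptive summary statistics will be displayed for subjects with at least one and frequency of health care resource utilizations", together with length of stay. It adds no further rule for merging records.

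**The concern.** The SAP expects overlapping records, because it has a rule for them. A patient is not in two hospital stays at once, so overlapping date intervals describe one continuous stay, possibly with a transfer inside it. The length-of-stay rule treats them in that way. The counting rule does so only when the start dates happen to coincide.

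The two variables, which are summarised together in 9.12.2, therefore rest on different ideas of what one hospitalization is. Pooling three forms makes overlap possible by design, since an ICU record for a relapse can sit inside the hospitalization recorded for that relapse. At stake is the accuracy of one descriptive count, which can be too high for subjects with such records.

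**Working it through.** The SAP states no figure to reproduce. The check applies the two rules of 5.7.2 to an example. The dates are illustrative and do not come from the SAP.

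**Inputs**
- Relapse summary form: hospitalized Days 100-110 (assumed).
- ICU form: Days 102-104 (assumed, and assuming that the form records the date of transfer to the ICU).
- Length per admission: end date - start date + 1 (5.7.2).
- Overlapping days counted once (5.7.2, length of stay only).
- Records merged if admission dates are identical (5.7.2, count only).

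**Length of stay, any hospitalization**
- Relapse record: 110 - 100 + 1 = 11 days.
- ICU record: 104 - 102 + 1 = 3 days, all within Days 100-110.
- Each day once: 11 + 3 - 3 = 11 days.

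**Number of hospitalizations**
- Admission days are 100 and 102. They differ, so nothing is merged and the count is 2.
- If the overlapping records are merged first, the count is 1 and length of stay is still 11 days.

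**How the result depends on the second date**

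| ICU record starts | Count under 5.7.2 | Length of stay |
|---|---|---|
| Day 100 | 1 | 11 days |
| Day 101 | 2 | 11 days |
| Day 102 | 2 | 11 days |

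(In each row the ICU record ends by Day 110.) In general, k overlapping records of one stay with k different admission dates give a count of k, while length of stay does not change. The same stay entered on two forms with the same admission date is merged correctly.

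**What else could move**
- Subjects with at least one hospitalization: unchanged, because a count of 1 or 2 is at least one either way.
- Single-form categories: affected only if one stay has several records with different dates within that category.
- Primary and secondary endpoints: not derived from this variable.

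**The case against.** The strongest defence is that the rule is a stated and reproducible convention. The variable is called a number of admissions or visits, not of continuous episodes, and the ICU form is listed on purpose as a source, so counting a transfer may be intended. Days and admissions may also use different units. This does not hold up. A same-day ICU admission is merged while a next-day one is counted again, and no coherent definition of an admission gives that result. ICU admissions already have their own category, and the merging rule itself speaks of one hospitalization.

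Other parts of the defence stand:

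- **The ICU example rests on an assumption.** The SAP does not say whether the ICU form holds the transfer date or the hospital admission date. If it holds the latter, the present rule already removes the duplicate.
- **Adverse events.** A reader might infer that an event arising in hospital adds an admission dated from its own onset. Section 5.5.7 gives only a yes/no item on whether the event required hospitalization. Nothing says that the onset date serves as an admission date, or that the item is answered yes for a patient already admitted.
- **Days per admission.** A reader might divide 11 days by 2 and conclude that mean stay is reported as 5.5 days. Section 9.12.2 plans no such ratio.
- **Which patients, and how many.** A reader might infer that the over-count concentrates in the most severe cases, or put a percentage on it. The SAP supports neither.

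**Conclusion.** The point holds in a limited form. As written, 5.7.2 can report one continuous stay as two or more hospitalizations when overlapping records carry different admission dates. The rule is stated and gives a wrong count in that case, so this is more than a missing detail. In the example the count is 2 for one 11-day stay.

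The reach is small. Only the descriptive frequency in 9.12.2 is affected, chiefly in the pooled category. No test in the multiple testing strategy of 9.1 uses it, and nothing in the SAP suggests that the two arms would be affected differently. The total effect cannot be estimated from the SAP: it depends on how often overlapping records occur and on which dates the forms hold, and it could be close to zero. This is a minor correction that is worth making because it is cheap.

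**What to change.** Add one sentence to 5.7.2: within each category, records whose date intervals overlap (the later one starts before the earlier one ends), or that have the same admission date, are merged into one hospitalization before counting, and both the count and the length of stay are derived from the merged intervals.

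Two details belong with it. Records that touch only on a day of discharge and readmission stay separate, so that a genuine readmission on that day is not lost. The existing rule that each day counts once is kept, so that this shared day is not added twice. ICU admissions remain their own category.

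The cost is small, because length of stay already requires overlapping intervals to be handled. One downside remains: a same-day transfer between hospitals would still count as two hospitalizations.

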5.8 Pharmacodynamic variables

Peripheral blood lymphocyte counts from central laboratory (absolute and change from baseline counts) are derived, as described in Section 5.5.12.

Lymphocyte counts are further categorized into the following categories:

- $< 0.2 \times 10^9/L$;
- $\geq 0.2 \times 10^9/L - < 0.5 \times 10^9/L$;
- $\geq 0.5 \times 10^9/L - < 0.8 \times 10^9/L$;
- $\geq 0.8 \times 10^9/L - < 1.0 \times 10^9/L$;
- $\geq 1.0 \times 10^9/L$.

Lymphocyte counts from central laboratory are flagged for analysis according to their sample dates as ‘Baseline’, ‘Last on treatment’, ‘Day-15 follow-up’, ‘Day-30 follow-up’, and ‘Last follow-up assessment’ following the rules described in Sections 5.5.1 and 11.4.

6 DEFINITION OF PROTOCOL DEVIATIONS

This section refers to all protocol deviations as recorded in the database following the specifications provided in the protocol deviation code list.

Protocol deviation ‘Study drug taken from non-allocated kit’ (PD_MM.058) will be classified at unblinding into the following two sub-protocol deviations: ‘Study drug taken from non-allocated kit: non-assigned treatment received’ (PD_MM.0581) or ‘Study drug taken from non-allocated kit: assigned treatment received’ at unblinding (PD_MM.0582).

Protocol deviations are categorized while being entered into the database into the following categories:

- **Important** protocol deviations (Yes/No)
- **Timing** (before Randomization / after Randomization / after end of treatment/ anytime during the study)

In addition, protocol deviations are categorized by high-level topic in line with the Protocol Deviation code list [see Appendix B].

